response/relapse < 6 mo), 42% had prior FCR or PCR and 21% had prior alemtuzumab. The TLS prevention strategy resulted in only 2 (3.8%) cases of TLS, both observed at 2.5 mg/daily (1 patient with Grade 2 and another with lab TLS). Grade 3/4 tumor flare occurred in 5 (9.6%) patients and was managed with NSAIDs or low-dose steroids. The most common Grade 3/4 adverse events (AEs) included neutropenia (65%) and thrombocytopenia (33%). Febrile neutropenia occurred in 4 (8%) patients. Grade 3/4 infections were observed in 21 (40%) patients; 10 (19%) patients developed pneumonia and 3 developed sepsis; 2 cases of sepsisrelated death at day 37 and 94 of therapy were also noted but deemed unrelated to study drug by the investigators. Reasons for study discontinuation included disease progression (37%), AE's (29%), consent withdrawal (15%), death (4%), other reasons (10%). For 16 (31%) patients, 2.5 mg/daily was the maximum dose reached and 22 (42%) patients were unable to escalate beyond 5 mg/daily. Grade 4 neutropenia was the primary reason for delay in dose escalation. By intentto-treat (ITT) analysis, 6 patients (12%) had a partial response (NCI-WG 1996), 30 patients (58%) had stable disease and 13 patients (25%) progressed; 3 patients were non-evaluable. Median duration of treatment was 3.1 months (range, 0.07-18.4) and the median time to response was 4.3 months (range, 2.8-7.4). Responses were observed at 10 mg/daily (n=3), at 15 mg/daily (n=1), and at 20 mg/daily (n=2); Median PFS (ITT) was 5.5 months and median PFS for responders was 12 months. Three patients still remain on therapy and were transferred to commercial lenalidomide. (Data on file at Celgene)

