21. APPENDICES

21.1. Adverse Event

An adverse event (AE) is any noxious, unintended, or untoward medical occurrence occurring at any dose that may appear or worsen in a subject during the course of a study. It may be a new intercurrent illness, a worsening concomitant illness, an injury, or any concomitant impairment of the subject's health, including laboratory test values (as specified by the criteria below), regardless of etiology. Any medical condition that was present prior to the signing of informed consent and that remains unchanged or improved should not be recorded as an AE. If there is a worsening of that medical condition, this should be considered an AE. A diagnosis or syndrome should be recorded on the AE page of the Case Report Form rather than the individual signs or symptoms of the diagnosis or syndrome.

All AEs will be recorded by the Investigator(s) from the signing of informed consent to the treatment discontinuation visit. All AEs that lead to study discontinuation should be followed until resolution or stabilization. For subjects who discontinue study treatment but continue to be followed every 28 days until PD or new CLL therapy, AEs will be reported until 30 days post last dose of study drug or until study discontinuation, whichever occurs last. SAEs will be reported from time informed consent form is signed to 30 days post last dose of study drug. SAEs will be reported at any time post last dose of study drug if it is considered related to study drug. AEs will be recorded on the AE page of the eCRF and in the subject's source documents.

Abnormal laboratory values defined as adverse events

An abnormal laboratory value is considered to be an AE if the laboratory abnormality is characterized by any of the following:

- Results in discontinuation from the study.
- Requires treatment, modification/interruption of study drug dose, or any other therapeutic intervention.
- Is judged by the Investigator(s) to be of significant clinical importance.

If a laboratory abnormality is one component of a diagnosis or syndrome, then only the diagnosis or syndrome should be recorded on the AE page of the eCRF. If the abnormality was not a part of a diagnosis or syndrome, then the laboratory abnormality should be recorded as the AE.

Serious adverse event

A serious adverse event (SAE) is any AE which:

- Results in death

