- Is life-threatening (i.e., in the opinion of the Investigator(s) the subject is at immediate risk of death from the AE)
- Requires inpatient hospitalization or prolongation of existing hospitalization
- Results in persistent or significant disability/incapacity (a substantial disruption of the subject's ability to conduct normal life functions)

- Is a congenital anomaly/birth defect
- Constitutes an important medical event

Important medical events are defined as those occurrences that may not be immediately life threatening or result in death, hospitalization, or disability, but may jeopardize the subject or require medical or surgical intervention to prevent one of the other outcomes listed above. Medical and scientific judgment should be exercised in deciding whether such an AE should be considered serious.

Second primary malignancies will be monitored as events of interest and must be reported as serious adverse events. This includes any second primary malignancy, regardless of causal relationship to study medication, occurring at any time for the duration of the study, from the time of signing the ICF up to and including any follow-up, observation and/or survival follow-up period. In this study, subjects will be followed until 80% of the subjects have progressed or died or up to five years after the last subject was randomized, whichever occurs later. Events of second primary malignancy are to be reported using the SAE report form and must be considered an "Important Medical Event" even if no other serious criteria apply; these events must also be documented in the appropriate page(s) of the CRF and subject's source documents. Documentation of the diagnosis of the second primary malignancy must be provided at the time of reporting as a serious adverse event (e.g., any confirmatory histology or cytology results).

Events not considered to be SAEs are hospitalizations which: were planned before entry into the clinical study; are for elective treatment of a condition unrelated to the studied indication or its treatment; occur on an emergency outpatient basis and do not result in admission (unless fulfilling other criteria above); are part of the normal treatment or monitoring of the studied indication and are not associated with any deterioration in condition.

If an AE is considered serious, both the AE pages of the eCRF and the SAE Report Form must be completed.

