### 3. INTRODUCTION

This document describes the statistical analyses and data presentations to be performed for protocol CC-5013-CLL-009 “A Phase 2, Multi-Center, Randomized, Double-Blind, Parallel-Group Study of The Safety and Efficacy of Different Lenalidomide (Revlimid®) Dose Regimens in Subjects with Relapsed or Refractory B-Cell Chronic Lymphocytic Leukemia”.

Subjects were randomized (1:1:1) in a double-blind fashion to the 5 mg, 10 mg, and 15 mg starting dose arms (treatment arm 1, treatment arm 2, and treatment arm 3 respectively).

The randomization procedure was accomplished by a validated interactive voice response system (IVRS). Subjects were stratified at randomization by (i) relapsed vs refractory to their last purine-analog or bendamustine based treatment regimen (if subject has received both, the status post most recent purine-analog or bendamustine regimen was used for stratification) and (ii) age < 65 years of age vs ≥ 65 years of age. The subjects received lenalidomide once daily in a 28 day cycle and will be escalated every 28 days as tolerated in a stepwise manner up to a maximum of 25 mg daily.

Depending on the starting dose, subjects were allocated in a double-blind fashion to three different regimens and will escalate every 28 days, based on individual subject tolerability, as follows:

- Treatment Arm 1: 5 mg →10 mg →15 mg →20 mg →25 mg/daily
- Treatment Arm 2: 10 mg →15 mg →20 mg →25 mg/daily
- Treatment Arm 3: 15 mg →20 mg →25 mg/daily

The primary objective of this study was to evaluate the safety of different lenalidomide dose regimens in subjects with relapsed or refractory B-cell chronic lymphocytic leukemia (CLL). The secondary objective was to evaluate the efficacy of different lenalidomide dose regimens in subjects with relapsed or refractory B-cell CLL.

This study was conducted using a randomized Bayesian schedule-administration design that jointly models toxicity/disease progression outcomes using an extension method. The object of interest was to determine if a particular treatment administration schedule is superior to other competing schedules. No treatment arm was stopped during the conduct of the study.

In total 104 subjects were enrolled into the study.

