## 7. SUBJECT DISPOSITION

For all subjects randomized, subject disposition will be summarized. Subject disposition includes the number of subjects in the following categories:

- ITT Population
- Safety Population

Reasons for treatment termination will be collected on the CRF and will be summarized for all randomized subjects with the following categories:

- Adverse events
- Disease progression
- Withdrew consent
- Death
- Lost to follow-up
- Protocol violation
- Other

A separate listing will be provided for subjects who did not receive at least one dose of study drug.

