### 12.1. Adverse Events

The adverse events of Neutropenia, Anemia and Thrombocytopenia will be analyzed according to the grading system as recommended by the IWCLL guidelines for the diagnosis and treatment of CLL (Hallek, 2008).

The adverse event of Tumor Lysis Syndrome (TLS) will be analyzed according to the grading system as recommended by Cairo-Bishop grading system.

Treatment emergent adverse events (AEs) will be summarized by treatment arm and overall. A treatment emergent adverse event is defined as any AE occurring or worsening on or after the first treatment of any study drug, and within 30 days after the last dose of the last study drug received. Adverse events will be presented in descending order of frequency (for all subjects) by SOC, and then within each SOC, by decreasing order of preferred term. Adverse events are documented on the CRF together with their severity, according to the NCI CTCAE version 3.0 or higher, also referred to as NCI toxicity grading. For the categorization of the adverse events, the MedDRA® dictionary (version 15.0) will be used.

AE frequency will be tabulated by body system, MedDRA preferred term for each treatment regimen during the Treatment Phase as well as for the Follow-up Phase when appropriate. In the by-subject analysis, a subject having the same event more than once will be counted only once and by the greatest severity. AEs will be summarized by worst NCI CTCAE version 3.0 grade. In the case that the AEs or event frequencies are judged to be clinically important, an exact test may be used to analyze the difference between the treatment arms. Events of interest will also be summarized by treatment cycles.

AEs leading to death or to discontinuation from treatment, events classified as NCI CTCAE version 3.0 Grade 3, 4, and 4 AEs, treatment-related events, serious adverse events (SAEs) and events of interest (including second primary malignancies) will be summarized separately.

Individual AE listings by subject will be provided.

As an exploratory analysis, AEs will be summarized by treatment arm and by subgroup (i.e., relapse vs. refractory, age <65 vs. age ≥65, lines of prior CLL treatment, gender).

Adverse events (AE) will be classified using the Medical Dictionary for Regulatory Activities (MedDRA) classification system. The severity of the toxicities will be graded according to the NCI CTCAE version 3.0 whenever possible.

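### Appendix 21.1 counts worsening of any pre-consent condition as an AE and does not exempt the CLL under study, so progression can enter several all-cause safety tables

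*Protocol*

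**What the plan says.** Appendix 21.1 of the protocol sets the recording rule. It starts from "Any medical condition that was present prior to the signing of informed consent". If that condition is unchanged or better it is not recorded. Otherwise: "If there is a worsening of that medical condition, this should be considered an AE". The disease under study is not set apart.

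The same appendix lists hospitalizations that are not serious adverse events. Those for the studied indication are left out only when they "are part of the normal treatment or monitoring of the studied indication and are not associated with any deterioration in condition". An admission for worsening CLL does not meet that condition.

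The primary endpoint is the type, frequency, severity and drug relationship of AEs (Protocol 7.1, SAP 5.2). SAP 12.1 plans separate summaries that include "AEs leading to death or to discontinuation from treatment", high-grade events and serious events. It names no progression terms to be removed or shown apart.

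Elsewhere the plan keeps the two outcomes distinct. Protocol 10.5 lists AEs and disease progression as different reasons for stopping drug. SAP 7 does the same: "Reasons for treatment termination will be collected on the CRF", with separate categories for each. SAP 3 describes a design that "jointly models toxicity/disease progression outcomes".

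**The concern.** Safety by starting dose is the primary question, and progression feeds the secondary efficacy endpoints. If progression is recorded as an AE, a difference in disease control between starting doses can appear as a difference in toxicity. The AE-to-discontinuation summary could also disagree with the disposition table, where the same subject is counted under disease progression. Because the text can be read either way, sites may record progression differently, and nothing in SAP 12.1 would remove that variation at the analysis stage.

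**Working it through.** The plan gives no expected AE rate by arm and no significance level for AE comparisons, so there is no figure to reproduce. The check is a reading of the text, then an illustration on assumed inputs.

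**1. Is there an exemption?** Appendix 21.1, Table 2 footnote t, Protocol 15.8 and SAP 12.1 are the places where one would stand. None of them exempts progression of the CLL.

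**2. Does progression fall in the AE window?** Drug is given until progression or unacceptable toxicity (Protocol 8.1.4). SAP 12.1 counts AEs up to 30 days after the last dose. Progression on drug therefore falls inside.

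**3. Which tables are exposed?**
- Any AE: hardly, because such rates are likely to be near 100% (assumed).
- Drug-related: largely not, because Appendix 21.1 classes an event sufficiently explained by an underlying condition as not suspected.
- Grade 3 or higher, serious, AE-to-discontinuation and AE-to-death: yes, when the recorded progression is graded, judged serious or actioned accordingly.

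**4. A Grade 3 or higher or serious-event table.** Let t be the true toxicity rate, equal in both arms, p the progression rate, and q the share of progressions that count in the table. With toxicity and progression assumed independent, the apparent rate is t + (1 − t) × q × p.

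Inputs: t = 40%, borrowed from Grade 3/4 infections in CLL-001 (21 of 52, Protocol 5.3.2.3). p = 25% from the same study (13 of 52) and 39% from one of the relapsed/refractory studies in Protocol 5.3.2.1 (17 of 44). Using these as two arms of this trial is an assumption. The 20% against 50% row is assumed outright.

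| t | q | p, two arms | Apparent rates | Gap, points (true gap 0) |
|---|---|---|---|---|
| 40% | 1 | 25%, 39% | 55.0%, 63.4% | 8.4 |
| 40% | 1/2 | 25%, 39% | 47.5%, 51.7% | 4.2 |
| 40% | 1/4 | 25%, 39% | 43.75%, 45.85% | 2.1 |
| 20% | 1 | 25%, 39% | 40.0%, 51.2% | 11.2 |
| 65% | 1 | 25%, 39% | 73.75%, 78.65% | 4.9 |
| 98% | 1 | 25%, 39% | 98.5%, 98.8% | 0.3 |
| 40% | 1 | 20%, 50% | 52.0%, 70.0% | 18.0 |

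First row: 0.40 + 0.60 × 0.25 = 0.550 and 0.40 + 0.60 × 0.39 = 0.634. With 35 per arm, t = 40% and q = 1, exact enumeration of Fisher's test at an assumed two-sided 0.05 rejects in 6.9% of trials for 25% against 39%, and in 25.8% for 20% against 50%. With progression equal at 25% it rejects in 2.5%.

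**5. The AE-to-discontinuation table, worst case.** Stop reasons are separate categories, so the rates add. CLL-001 reports 37% stopping for progression and 29% for AEs (Protocol 5.3.2.3): about 19 + 15 = 34 of 52, or 65% (66% from the rounded figures). Keep AE stops at 29% in both arms, assume that every progression stop is also entered as an AE leading to discontinuation, and let progression stops differ around 37%:

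| Progression stops | Table would read | Gap, points | Fisher rejection |
|---|---|---|---|
| 32%, 42% | 61%, 71% | 10 | 10% |
| 27%, 47% | 56%, 76% | 20 | 34% |
| 22%, 52% | 51%, 81% | 30 | 70% |

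For the middle row the standard error is √(0.56 × 0.44/35 + 0.76 × 0.24/35) = 0.111, or 11 points. None of these arm gaps comes from the documents.

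**The case against.** The strongest reply is that this is a missing clarification and not an instruction to record progression. The examples of an AE in Appendix 21.1 read "It may be a new intercurrent illness, a worsening concomitant illness, an injury", which points to illness other than the disease under study. The words about etiology close that sentence and do not qualify the worsening rule. Progression has its own channel: response assessment, adjudication, a separate stop reason, and deaths by primary cause (SAP 12.5). AEs are tabulated by preferred term, so a progression term would be visible. CRF completion instructions, which might settle the matter, are not among the documents.

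Much of this stands, and it limits the size. It does not close the gap. The operative sentence covers any condition, the list is only illustrative, and the hospitalization exception shows that the drafters named the studied indication when they meant it. The visible preferred term helps with the by-term table. It does not correct a count of subjects with at least one serious or high-grade event, since the same subject may have others.

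Two further objections hold. Earlier progression shortens exposure and so lowers other AE counts, which makes the net direction uncertain. The exact test on AEs in SAP 12.1 is optional, so the rejection rates above describe a test that may never be run.

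A reader might go further in two ways that the documents do not support. One is that each progression automatically becomes a Grade 3 or higher or serious event. Appendix 21.1 grades severity on symptoms and requires a listed criterion for seriousness, and progression need not meet either. The other is that one event is counted on both sides of the interim toxicity and progression comparison. That depends on the interim toxicity definition, which is blacked out in SAP 6.3 and 14.2. SAP 3 also states that no arm was stopped.

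**Conclusion.** The point holds as a gap in the recording rule and in SAP 12.1. Following the text can put an efficacy outcome into four all-cause summaries of the primary safety endpoint, and the analysis plan has no step that separates it again.

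How much it matters cannot be known from the documents. It depends on how many sites record progression as an AE, how it is graded, and how far progression differs between arms. With equal toxicity of 40% and progression of 25% against 39%, the spurious gap is about 2 to 8 points as the counted share rises from a quarter to all; lower true toxicity makes it larger, and higher makes it smaller. A gap of 20 points or more in the discontinuation table needs both universal recording and an equally large difference in progression stops. The case for acting is that the remedy is cheap and loses nothing.

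**What to change.** In SAP 12.1, before database lock, list the preferred terms that denote progression of the study CLL. Present the Grade 3 or higher, serious, AE-to-discontinuation and AE-to-death summaries by arm both with and without those terms, with progression on its own line. Showing both versions avoids deleting primary-endpoint data after unblinding. SAP 3 says the plan is finalized before the lock for the PFS analysis, so the list can be fixed in time.

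In Appendix 21.1, add one sentence that states how progression of the study CLL is to be recorded, so that sites are consistent and the rule agrees with the separate stop reasons in Protocol 10.5 and SAP 7. The last subject was randomized in 2012 and few remain on drug (Amendment 6 summary), so this sentence will affect little new data. The SAP change does most of the work.

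The cost is a term list and a few extra tables. Deaths from CLL remain in the OS analysis and in the tables of SAP 12.5.

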21.2. Declaration of Helsinki

The Declaration of Helsinki can be found at: http://www.wma.net/e/policy/b3.htm

21.3. Cairo-Bishop Definition and Grading of Tumor Lysis Syndrome (Cairo, 2004)

Cairo-Bishop Definition of Laboratory Tumor Lysis Syndrome (LTLS)

Uric Acid	\geq 476 µmol/l (\geq 8.0 mg/dl) or 25% increase from baseline	
Potassium	\geq 6.0 mmol/l (\geq 6.0 mEq/l) or 25% increase from baseline	
Phosphorous	\geq 1.45 mmol/l (\geq 4.5 mg/dl) or 25 % increase from baseline	
Calcium	\leq 1.75 mmol/l (\leq 7.0 mg/dl) or 25% decrease from baseline	ON

Laboratory tumor lysis syndrome (LTLS) is defined as either a 25% change or level above or below normal, as defined above, for any two or more serum values of uric acid, potassium, phosphate, and calcium within 3 days before or 7 days after the initiation of chemotherapy. This assessment assumes that a patient has or will receive adequate hydration (\pm alkalinization) and a hypouricaemic agent(s).

Cairo-Bishop Definition of Clinical TLS

The presence of laboratory TLS and one or more of the following criteria:

- 1. Creatinine: ≥ 1.5 ULN (age ≥ 12 years or age adjusted)
- 2. Cardiac arrhythmia / sudden death
- 3. Seizure*

ULN, Upper limit of normal

Cairo-Bishop Grading System for TLS

Grade	LTLS	Creatinine	Cardiac Arrythmia	Seizure
0	-	≤1.5 x ULN	None	None
1	+	1.5 x ULN	Intervention not indicated	None
2	+	> 1.5 – 3.0 x ULN	Non-urgent medical intervention indicated	One brief generalized seizure; seizure(s) well controlled or infrequent; focal motor seizures not interfering with ADL
3	ţC)	> 3.0 – 6.0 x ULN	Symptomatic and incompletely controlled medically or controlled with device	Seizure in which consciousness is altered; poorly controlled seizure disorder; breakthrough generalized seizures despite medical intervention
4	+	> 6.0 x ULN	Life-Threatening	Seizures of any kind that are prolonged, repetitive, or difficult to control
5	+	Death*	Death*	Death*

LTLS, laboratory tumor lysis syndrome; ULN, upper limit of normal; ADL, activities of daily living

^{*}Not directly attributable to a therapeutic agent

^{*}Probably or definitely attributable to clinical TLS

